17.3 Statistical Methods

17.3.1 Qualitative Analyses

17.3.1.1 Phase 1

Content analysis (Krippendorff, 2018) supplemented with QSR NVivo software version 10 (Doncaster, Victoria, Australia) will be used to generate interview response themes. The interviews will be audiotaped and professionally transcribed by a vendor approved by Mayo Clinic with a written transcript generated for each. If the participant was not comfortable being recorded, or the audio equipment was malfunctioning, the interviewer's written notes will be imported to NVivo for analysis. Two study team members will review and code the data. Initially, the coders will read 8 transcripts from the AIAN participants to decide whether 12 AIAN participants will reach data saturation. Next, 6 transcripts (~20%) will be randomly selected (3 each from the AIAN women and interested party groups respectively). These will be independently and deductively coded (Saldana, 2016) to generate code lists based on the interview content domains. These codes will be compared and reconciled before arriving at the final set of codes and the coders are calibrated. A third study team member will be brought in to aid in reaching consensus if needed. At this point, a codebook will be developed which will describe the meaning of each code and include relevant key words from the transcripts that link to each code (Miles et al., 2014). To aid in the assessment of the "acceptability" of the postings, within each code, valence coding will also be employed when relevant to track whether responses to that code are positive, negative, mixed, or neutral. The codebook will then be reviewed by the third study team member for feedback and refinement. The final codes will then be applied to all data.

Two study team members will code all interviews. The third team member will resolve discrepancies as needed until consensus is reached. The benefit of coding jointly is that there is ongoing rich discussion of the coding process, of new themes emerging from the data with continual updates of the codebook themes and keywords, and quality control of the coding process, with one person coding into NVIVO and the other person observing the coding to make sure errors are not made (Coffey & Atkinson, 1996; Patton, 2015; Wolff et al., 2019). As a part of the dual coding process, the coders will write up memos each time they meet to code. The memo-writing will be the place where discovery of patterns across themes is recorded. Through discussion ideas about potential patterns and themes will be discussed and reports will be generated using NVIVO to further explore such themes and patterns. At the end of coding, the third study team member will be asked to randomly review 5 of the interviews to assess agreement with the coding.

For AIAN women participants who give permission to be re-contacted, we will review her individual transcript (responses) and how these were interpreted (coded) (i.e., member checking). Responses will be entered and coded using the same methods as the preliminary analysis. We will conduct further qualitative analyses if there are disconfirming voices or themes where participants could not recognize or relate to the interpretations provided and/or to explore any new concepts reported.

Coded data will be examined for patterns across the AIAN women and interested party groups; as well as among AIAN women, any patterns in themes by age group, or substance use.

The qualitative findings will be discussed with the CAC who will guide us in the interpretation and integration of findings and resolving any discrepancies in themes for the AIAN women and stakeholder groups. In the LI's formative work to develop a social media intervention for nicotine use among Alaskan AIAN adults (Merculieff et al., 2021), differences were not found between AIAN smokers or community stakeholders in the acceptability of content (moderator postings) based on cultural relevance or perceived effectiveness. In addition to the feedback on the moderator postings, we expect the interested parties will provide unique information on how the intervention can best be promoted to engage AIAN women to participate in the study as well as factors in designing the intervention that would make the intervention appealing for sustained use within AIAN healthcare and community settings.

17.3.1.2 Phase 3

Survey: The Follow-up Survey contains four open-ended questions assessing the participant's experiences with the intervention, their recommendations for improving the intervention, and their thoughts on using the Facebook group as a way to learn how to mentor other AIAN women who are engaging in illicit opioid use to start their recovery. The text of survey responses will be entered into an Excel spread sheet for analysis. Analyses will generally follow the procedures described for Phase 1. Content analysis (Krippendorff, 2018) supplemented with QSR NVivo software version 10 (Doncaster, Victoria, Australia) will be used to generate response themes in the data for each of the three survey items. Coded data will be examined for any patterns in themes by age group, and substance use.

Facebook intervention group comments and postings: The text of participant-generated posts and comments will be exported into an excel spreadsheet for analysis of content. We will identify common themes of response in the data using content analysis (Krippendorff, 2018) supplemented with QSR NVivo software version 10 (Doncaster, Victoria, Australia). Analyses will generally follow the procedures described for Phase 1. We will summarize the major themes, and the frequency of topics discussed in participant comments and postings will be displayed graphically.

17.3.2 Quantitative Analyses

17.3.2.1 Primary Outcome: A culturally relevant Facebook intervention prototype to support recovery from opioid use.

The cultural relevance of the Facebook group will be determined by valence coding with QSR NVivo software version 10. We will summarize the expected outcomes for the development of the intervention using descriptive statistics (frequencies, percentage) which are the development and refinement of the content library (yes/no), development and refinement of the Facebook intervention prototype (yes/no), development and refinement of the intervention moderator guidelines (yes/no), and intervention moderators trained (yes/no). We expect that all outcomes will be achieved at 100% implementation.

17.3.2.2 Secondary Outcomes: Recruitment feasibility, study retention, level of intervention engagement, and intervention satisfaction.

We will summarize the number of potential participants screened, number eligible, reasons for ineligibility and number enrolled out of those eligible (i.e., participation rate) using frequencies and percentages. Baseline characteristics will be summarized using descriptive statistics (means, medians, frequencies, and percentages). We will summarize the number of enrolled women reporting other substance use at baseline and at follow-up. Study retention will be summarized as the percentage of enrolled participants completing the end of intervention survey and a UDS. The Social Media Usability scale (Lund, 2001) scores will be summarized using descriptive statistics (mean, standard deviation, median and range).

The level of intervention engagement will be summarized using descriptive statistics (medians, frequencies, and percentages). The number of *posts* 'seen by' group members, their reactions, and comments will be summarized. We will also summarize participant-level engagement metrics (e.g., comments, reactions) and the total engagement count overall. The analyses will use an intent-to-treat approach including all 10 participants with those never having engaged in the Facebook group receiving a total engagement count of zero. We will describe patterns of engagement by age group (with age based on median split or <40 vs. ≥ 40 years depending on the age distribution), substance use endorsed on the TLFB (any use: yes/no and/or median split of # of substances used) at baseline and follow-up, and relapse to opioid use (yes/no). We will summarize the total engagement count for moderator and participant-generated posts, respectively.

17.3.2.3 Exploratory Outcomes: Abstinence from opioid use and MOUD retention at the end of the intervention.

Descriptive statistics (percentages and frequencies) will be used to summarize the sample for relapse to opioids, operationalized as either a positive opiate or fentanyl UDS with missing UDS test imputed as positive **or** self-report of any illicit opioid use in the past 30 days or since study enrollment. Secondarily we will summarize relapse as at least seven consecutive days of self-reported illicit opioid use in the past 30 days or since study enrollment (Nunes et al., 2018). Secondarily, we will also summarize outcomes considering missing UDS as missing and not positive (King et al., 2020).

From the TLFB, will summarize MOUD retention as the proportion of days reporting MOUD use and current use using descriptive statistics (percentages and frequencies).

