Study Population	We will enroll up to 18 AIAN participants and 12 interested parties for the qualitative interview phase, and 10 different AIAN participants for the beta-testing phase. The AIAN participants will be women at least 18 years of age who reside in Minnesota, have opioid use disorder (OUD) with at least one month of opioid abstinence and are currently receiving MOUD. The interested parties will be health care providers or AIAN community partners with knowledge of AIAN culture and/or OUD treatment and recovery among AIAN people.
Phase or Stage	I

Description of Sites/Facilities Enrolling Participants	The study site is Mayo Clinic. AIAN women with OUD will be referred to this study by clinicians and staff from addiction treatment programs, community organizations and programs in and surrounding Minneapolis, Minnesota, United States, and community flyers. Interested parties will be referred primarily by our CAC.
Description of Study Intervention/Experimental Manipulation	During the qualitative phase, feedback from individual interviews with AIAN women and stakeholders will be used to develop the intervention. The web-based study intervention to be developed will be a private, hidden, moderated, Facebook group that will be active for 3 months. Moderators will post content every 1-2 days from a content library of about 30 postings each repeated twice during the 3 months. Content (moderator postings) will consist of pictures/images combined with text and videos designed to provide information and stimulate participant discussion. The intervention will be beta-tested for a 30-day period using a single arm design with assessments conducted at baseline and at the end of the intervention.
Safety Reporting	Adverse Events (AEs) and Serious Adverse Events (SAEs) that occurred within the 30-day intervention period will be self-reported by the participants in the follow-up visit.
Analyses	In the qualitative interview phase, content analysis supplemented with QSR NVivo software will be used to generate interview response themes. In the beta-testing phase, descriptive statistics will be used to summarize the sample for baseline demographic characteristics, study retention, treatment satisfaction ratings, intervention engagement level, MOUD retention, and opioid relapse, operationalized as opioid positive urine or any self-reported illicit opioid use at follow-up.

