7.3. Exploratory Outcome Measures

Abstinence from illicit opioid and other substance use will be assessed using the Timeline Follow-Back (TLFB) interview (Sobell & Sobell, 1992; Wray et al., 2016) and a UDS at the end of the intervention. Relapse will be operationalized as either a positive opioid UDS **or** self-report of any illicit opioid use in the past 30 days or since study enrollment. Secondarily, we will summarize relapse as at least seven consecutive days of self-reported illicit opioid use in the past 30 days or since study enrollment (Nunes et al., 2018). Secondarily, we will also report outcomes considering missing UDS as missing and not positive/negative (King et al., 2020). MOUD retention will be assessed using the TLFB at the end of intervention visit and summarized as the proportion of days reporting MOUD use and current use.

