10.3.1. Screening Visits and Consent Procedures

10.3.1.1. Phone Screen

The study staff will either call the participant or vice versa to begin the screening process. They will first confirm their identity with their full name provided in their email or voicemail. Trained female study staff will screen interested participants by phone to determine the study eligibility criteria with an initial set of questions. The initial set of eligibility questions will include self-reported race/ethnicity, gender identity, age, current residence, OUD DSM-5 Checklist, current use of MOUD, comfort reading and speaking English, whether the individual has a Facebook account or is willing to set one up, access to broadband Internet at any location, and willingness to travel to a community clinic in Minneapolis for the UDS. If the individual is eligible for the study, study staff will give them the option to sign the informed consent form remotely using DocuSign via PTrax or meet the study staff at the Indian Health Board community clinic to sign a hard copy of the consent form before the UDS. In addition to the study eligibility criteria, participants will be asked if they have a current prescription for opioids on the Screening Form, but this information is neither an inclusion or exclusion criterion and will only be utilized in case their urine is positive for opioids in the UDS.

At the UDS screening visit, the remaining screening procedures will include the same suicidality questions from Phase 1 and the TLFB to assess past 30 day use of opioids such as oxycodone, opiates such as heroin, and fentanyl. Those not meeting these criteria will be provided with referral resources. For those meeting the study eligibility criteria study staff will complete a Participant Contact Form. This form collects the participant's email address and phone numbers as well as secondary contact information. No information from this form is used in data analyses, nor is this information captured in the data capture system.

The study staff member will then schedule the participant for a UDS to screen them for the presence of opiates, opioids, and fentanyl. They will be asked to bring their prescription bottle to the UDS to verify that they are taking MOUD, and, if the participant indicates that they have a prescription for opioids at screening, they will be asked to bring their opioid prescription bottle as well.

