The potential participant will have a private space away from the study staff to urinate into the test cup, which will have a thermometer strip attached to confirm that the sample is in the area of biological acceptance. The study staff will be required to wear protective clothing and gloves and treat it as an infectious agent. The study staff will use a script to instruct the potential participant on the minimum amount of urine necessary, that they should wash their hands after completing the sample, and how the study staff will read the result. The script will also reassure the potential participant that the urine sample will be destroyed after receiving the result, only the result will be kept if they are eligible, and they will receive a \$ [REDACTED] cash card for their time.

The study staff will use IDTC-II 12 Panel Instant Drug Test Cards [REDACTED] to test for recent (2-3 day window) substance use including opiates. The test will also detect amphetamine, barbiturates, buprenorphine, benzodiazepines, cocaine, methadone metabolite, methamphetamine, ecstasy, methadone, morphine, oxycodone, phencyclidine, tricyclic antidepressants, and marijuana. A separate drug test strip, the Instant Drug Test II Fentanyl, will be used to test for fentanyl (<https://cliawaived.com/fentanyl-rapid-tests-20.html>). The result for each substance measured with the IDTC-II cards can be "preliminary positive", "negative", or "invalid". The result for the Instant Drug Test II Fentanyl can be "positive," "negative," or "invalid." The study staff will be able to determine the presence of opiates and opioids within 5-60 minutes. If the result for opiates is "preliminary positive," the woman will not be eligible for the study, and she will be provided referral resources. The UDS will only be used for research purposes, so the study staff will not share the specimen and pursue confirmation testing with a third party (i.e., CLIAwaived, Inc.). The specimen will only be used by the study staff and promptly destroyed after receiving the results.

If the urine sample result is "preliminary positive" for opioids, the woman will confirm that she has been prescribed opioids for medical use, and will show her prescription to the study staff. The purpose of presenting the prescription bottle is to support the participant's self-report of having a prescription for opioids. However, a limitation is that we will not know if the amount of medication

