consumed exceeds the prescribed amount. If they do not have a prescription, they will not be eligible for this study and will be provided referral resources.

The test will detect other commonly abused substances besides opiates, and the full results will be used to characterize the sample at baseline. Any other positive result besides opiates and opioids will be neither an inclusion nor exclusion criterion or outcome measure. Eligible participants may complete the baseline survey with the study staff immediately after the UDS during this visit, or it will be scheduled to be completed by phone in the near future. Participants will receive a \$50 cash card for completing the UDS as a thank you for their time and for any travel costs incurred.

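### The urine arm of relapse is opiate-or-fentanyl in Section 17.3.2.3 but opioid in Section 7.3 and the synopsis, and none of the three sets aside a positive explained by a prescription

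*Combined protocol and SAP*

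**What the plan says.** Three places define relapse on the urine drug screen (UDS).

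- Section 17.3.2.3: "operationalized as either a positive opiate or fentanyl UDS with missing UDS test imputed as positive", or self-report of illicit opioid use.
- Section 7.3: "Relapse will be operationalized as either a positive opioid UDS", or self-report of illicit opioid use.
- Synopsis (Section 2.0, Analyses): "opioid relapse, operationalized as opioid positive urine or any self-reported illicit opioid use at follow-up".

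Other sections bear on what these words cover.

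- Section 10.3.1.1 describes the screening timeline interview as covering "past 30 day use of opioids such as oxycodone, opiates such as heroin, and fentanyl", so the three classes are named separately.
- Section 10.3.1.2 says of the card: "The test will also detect amphetamine, barbiturates, buprenorphine, benzodiazepines, cocaine, methadone metabolite, methamphetamine, ecstasy, methadone, morphine, oxycodone", among others. Fentanyl is on a separate strip.
- The same section states: "Any other positive result besides opiates and opioids will be neither an inclusion nor exclusion criterion or outcome measure". By implication, both opiates and opioids are outcome results.
- For an opioid-positive screening urine, Section 10.3.1.2 says that "the woman will confirm that she has been prescribed opioids for medical use, and will show her prescription to the study staff". Without a prescription she is not eligible.
- Section 10.3.8 applies the screening UDS procedures to the follow-up UDS.

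The exploratory objective (Section 5.3) and the synopsis outcome concern illicit opioid use. Section 17.1.2 and the heading of Section 17.3.2.3 leave out the word illicit.

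**The concern.** An analyst working from Section 17.3.2.3 and one working from Section 7.3 could classify the same woman differently. The protocol itself does not use opiate and opioid as synonyms, so the difference in wording cannot simply be ignored.

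The prescription case matters more. In all three definitions, illicit qualifies the self-report arm but not the urine arm. A woman admitted with a prescription-explained opioid positive who gives the same result at follow-up has not changed. Yet Section 7.3 and the synopsis would report her as relapsed, in a table that is meant to describe illicit use.

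Relapse (yes/no) is also one of the variables by which Section 17.3.2.2 describes engagement, so a misclassified woman would appear in the wrong group there too.

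**Working it through.** The plan states no relapse rate, power or precision for this outcome, and N=10 rests on precedent (Section 17.2.2.2). There is no planned figure to reproduce, so the check compares the definitions case by case.

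**Step 1. Meaning of opioid in Section 7.3 and the synopsis.** It has to be an umbrella term. If it had only the narrow sense of Section 10.3.1.1 (oxycodone-type drugs), Section 7.3 would leave out heroin and fentanyl.

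**Step 2. Apply each definition.** Assume the UDS is not missing, no illicit use is self-reported, and oxycodone has its own reading.

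| Follow-up urine | Section 7.3 and synopsis | Section 17.3.2.3, literal |
|---|---|---|
| Opiate or fentanyl positive, no prescription | relapse | relapse |
| Oxycodone-only positive, no prescription | relapse | not relapse |
| Oxycodone-only positive, prescription shown | relapse | not relapse |
| Opiate or fentanyl positive, prescription shown | relapse | relapse |
| Negative for all | not relapse | not relapse |

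The definitions disagree in rows 2 and 3. In row 3, Section 17.3.2.3 spares the woman only because the analyte is not listed, not because the drug was prescribed. In row 4 all three count a prescribed drug as relapse, since none limits the urine arm to illicit use.

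**Step 3. Is oxycodone read separately?** Section 10.3.1.2 refers to a result for each substance measured, which suggests that it is. But the card is called a 12-panel and the text names opiates plus 14 further substances, 15 in all. Separate reading is therefore suggested but not established.

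**Step 4. Size.** With N=10 (Section 8.2), the shift per affected woman is 100 × 1/10 = 10 percentage points. If nobody else relapses, the result is 0/10 = 0% (exact 95% interval 0 to 30.8%) under one definition and 1/10 = 10% (0.3 to 44.5%) under the other. The documents do not allow the number of affected women to be estimated.

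**The case against.** The strongest reply is that Section 17.3.2.3 is shorthand. It may simply name the two devices in Section 10.3.1.2: a card introduced as testing for opiates, and a fentanyl strip. That section treats opiates and opioids together as outcome results. The follow-up timeline interview also asks about opioids, opiates and fentanyl (Section 10.3.8), so a woman who discloses illicit oxycodone use is relapsed under every definition. This stands as far as it goes: a different result needs an undisclosed oxycodone-only positive and a separate reading. But if it is shorthand, the analysis section should not be the place where the analyte list is shorter.

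On prescriptions, the reply is that the objective says illicit and Section 10.3.8 already brings the prescription check to follow-up. That is correct, and the information may well be collected. However, the only stated consequence of the check is eligibility. No sentence links it to how relapse is coded.

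A reader might go further and infer that opioid in Section 7.3 counts a woman's own methadone or buprenorphine as relapse, since both are on the card and every participant receives MOUD. The documents do not support that reading. Section 8.3.2 requires both a negative urine opioid screen (criterion 6) and current MOUD (criterion 7). If own MOUD counted as an opioid positive, women taking methadone or buprenorphine would fail screening. A clarifying clause is worth having, but no effect size should be attached to this reading.

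**Conclusion.** The point holds as a minor inconsistency, with moderate confidence. Two things are wrong as written: the analyte wording differs between Section 17.3.2.3 and the other two definitions, and no definition separates a prescription-explained positive from illicit use.

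Each affected woman changes the relapse proportion by 10 percentage points at N=10. How many are affected is unknown and may be none. The oxycodone part assumes a separate reading on the card and no self-reported illicit use. The prescription part assumes that a woman with a prescribed opioid is enrolled, or starts one during the study, and tests positive at follow-up.

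It would be wrong to infer that the study's conclusions are at risk. The outcome is exploratory and descriptive, and no test, primary outcome or secondary outcome is defined by it. Its one further use is as a descriptive grouping variable for engagement. The rule for a missing UDS is not at issue here.

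The eligibility text is a separate item. Criterion 6 requires a negative urine opioid screen, while Section 10.3.1.2 allows an opioid positive with a prescription. These must be reconciled, and the answer affects how often the prescription case can arise.

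**What to change.** 1. Put one definition of UDS relapse, word for word, in the synopsis, Section 7.3 and Section 17.3.2.3. Give one analyte list that covers opiates, opioids other than MOUD such as oxycodone, and fentanyl. Add a clause that the participant's own MOUD is not counted.
2. Use the prescription check that Section 10.3.8 carries to follow-up. Report prescription-explained positives as a separate count and not as relapse to illicit use. If preferred, also show the result with them counted. The screening text describes the check for opioid positives only, so state which analytes the coding rule covers; the documents do not settle this.
3. Use the word illicit consistently in Section 17.1.2 and in Section 17.3.2.3, including its heading.
4. Separately, reconcile criterion 6 of Section 8.3.2 with the prescription allowance in Section 10.3.1.2.

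The cost is wording, plus one prescription field on the follow-up UDS form if it is not already there. No new test or visit is needed. The drawback, which Section 10.3.1.2 itself acknowledges, is that a shown prescription does not rule out use above the prescribed amount. The separate count keeps those results visible.
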